5.2 Exclusion criteria

Subjects meeting any of the following criteria are not eligible for inclusion in this study

1. Subjects with total ankylosis of the spine
2. Chest x-ray or MRI with evidence of ongoing infectious or malignant process obtained within 3 months of screening and evaluated by a qualified physician
3. Subjects taking moderate and high potency opioid analgesics (e.g. methadone, hydromorphone, morphine)
4. Presence of significant medical problems which at investigator's discretion, will prevent the subject from participating in the study, including but not limited to the following: Subjects with severely reduced kidney function (estimated glomerular filtration rate (eGFR) < 29 ml/min/1.73m²), history of renal trauma, glomerulonephritis, or patients with one kidney only, or a serum creatinine level exceeding 1.5 mg/dl (132.6 μ mol/L)
5. Any therapy by intra-articular injections (e.g. corticosteroid) within 4 weeks before Randomization
6. Underlying conditions (including, but not limited to metabolic, hematologic, renal, hepatic, pulmonary, neurologic, endocrine, cardiac, infectious or gastrointestinal) which in the opinion of the investigator significantly immunocompromises the subject and/or places the subject at unacceptable risk for receiving an immunomodulatory therapy
7. Any medical or psychiatric condition which, in the Investigator's opinion, would preclude the participant from adhering to the protocol or completing the study per protocol
8. Active systemic infections during the last two weeks (exception: common cold) prior to randomization or any infection that reoccurs on a regular basis
9. History of ongoing, chronic or recurrent infectious disease or evidence of tuberculosis infection as defined by either a positive purified protein derivative (PPD) skin test (the size of induration will be measured after 48-72 hours, and a positive result is defined as an induration of ≥ 5 mm or according to local practice/guidelines) or a positive QuantiFERON TB-Gold test as indicated in the assessment schedule in [Table 8-1](#). Subjects with a positive test may participate in the study if further work up (according to local practice/guidelines) establishes conclusively that the subject has no evidence of active tuberculosis. If presence of latent tuberculosis is established, then treatment according to local country guidelines must have been initiated
10. Past medical history of infection with HIV or hepatitis B prior to randomization or active infection or on treatment for Hepatitis C at randomization

11. History of lymphoproliferative disease or any known malignancy, or history of malignancy of any organ system treated or untreated within the past 5 years, regardless of whether there is evidence of local recurrence or metastases (except for skin Bowen's disease, or basal cell carcinoma or actinic keratoses that have been treated with no evidence of recurrence in the past 12 weeks; carcinoma in situ of the cervix or non-invasive malignant colon polyps that have been removed)
12. Use or planned use of prohibited concomitant medication (see [Section 6.2.2](#))
13. Inability or unwillingness to undergo repeated venipuncture (e.g., because of poor tolerability or lack of access to veins)
14. Pregnant or nursing (lactating) women, where pregnancy is defined as the state of a female after conception and until the termination of gestation, confirmed by a positive hCG laboratory test
15. History or evidence of ongoing alcohol or drug abuse, within the last six months before randomization
16. Screening total WBC count <3,000/ μ l, or platelets <100,000/ μ l or neutrophils <1,500/ μ l or hemoglobin <8.5 g/dl (85 g/L)
17. History of clinically significant liver disease or liver injury indicated by abnormal liver function tests, such as SGOT (AST), SGPT (ALT), alkaline phosphatase and serum bilirubin. The investigator should be guided by the following criteria:
 - Any single parameter may not exceed 2 x the upper limit of normal (ULN). A single parameter elevated up to and including 2 x ULN should be re-checked once more as soon as possible, and in all cases, at least prior to randomization, to rule-out laboratory error.
 - If the total bilirubin concentration is increased above 2 x ULN, total bilirubin should be differentiated into the direct and indirect reacting bilirubin. In any case, serum bilirubin should not exceed the value of 1.6 mg/dL (27 μ mol/L)
18. Significant medical problems or diseases, including but not limited to the following: uncontrolled hypertension (\geq 160/95 mmHg), congestive heart failure (New York Heart Association status of class III or IV), uncontrolled diabetes, or very poor functional status precluding ability to perform self-care
19. Plans for administration of live vaccines during the study period or within 6 weeks prior to randomization
20. Women of child-bearing potential, defined as all women physiologically capable of becoming pregnant, unless they are using effective methods of contraception during the entire study or longer if required by locally approved prescribing information (e.g., 20 weeks in EU). Effective contraception methods include:
 - Total abstinence (when this is in line with the preferred and usual lifestyle of the subject. Periodic abstinence (e.g., calendar, ovulation, symptothermal, post-ovulation methods) and withdrawal are not acceptable methods of contraception
 - Female sterilization (have had surgical bilateral oophorectomy with or without hysterectomy) or tubal ligation at least six weeks before taking study treatment. In case of oophorectomy alone, only when the reproductive status of the woman has been confirmed by follow up hormone level assessment

- Male sterilization (at least 6 months prior to screening). For female subjects on the study, the vasectomized male partner should be the sole partner for that subject
- Barrier methods of contraception: Condom or Occlusive cap (diaphragm or cervical/vault caps). For UK: with spermicidal foam/gel/film/cream/ vaginal suppository
- Use of oral, injected or implanted hormonal methods of contraception or other forms of hormonal contraception that have comparable efficacy (failure rate <1%), for example hormone vaginal ring or transdermal hormone contraception
- Placement of an intrauterine device or intrauterine system

In case of use of oral contraception women should have been stable on the same pill for a minimum of 3 months before taking study treatment.

Women are considered post-menopausal and not of child bearing potential if they have had 12 months of natural (spontaneous) amenorrhea with an appropriate clinical profile (e.g., age appropriate, history of vasomotor symptoms) or have had surgical bilateral oophorectomy (with or without hysterectomy) or tubal ligation at least six weeks prior to randomization. In the case of oophorectomy alone, only when the reproductive status of the woman has been confirmed by follow up hormone level assessment is she considered not of childbearing potential.

21. Active ongoing inflammatory diseases other than axSpA that might confound the evaluation of the benefits of secukinumab therapy, including inflammatory bowel disease or uveitis
22. Current severe progressive or uncontrolled disease which in the judgment of the clinical investigator renders the subject unsuitable for the trial
23. Use of other investigational drugs at the time of enrollment, or within 5 half- lives of enrollment, or within 4 weeks until the expected pharmacodynamic effect has returned to baseline, whichever is longer; or longer if required by local regulations
24. History of hypersensitivity to any of the study drug constituents
25. Previous exposure to secukinumab (AIN457) or any other biologic drug directly targeting IL-17 or the IL-17 receptor
26. Previous treatment with any cell-depleting therapies including but not limited to anti-CD20 or investigational agents (e.g., CAMPATH, anti-CD4, anti-CD5, anti-CD3, anti-CD19)

6 Treatment

6.1 Study treatment

6.1.1 Investigational and control drugs

Novartis will supply the following study treatments:

Investigational Treatment:

- Secukinumab liquid in vial (LiV) for i.v. infusion provided in glass vials, [REDACTED]

Reference Therapy:

- Secukinumab placebo [REDACTED] for i.v. infusion provided in 5 mL LiV.

The LiV glass vials are packed in double-blind (treatment period 1, up to and including Week 12) and open label fashion (treatment period 2, from Week 16 onwards). For detailed instructions for storage, handling and administration of study treatment, please refer to the Pharmacist Manual.

The study medication will be labeled as follows:

- Double blind Secukinumab Liquid in Vial will be labeled as AIN457 [REDACTED] [REDACTED] Placebo.
- Open label Secukinumab Liquid in Vial will be labeled as AIN457 [REDACTED]

6.1.2 Additional study treatments

No other treatment/s beyond investigational drug and control drug are included in this trial.

6.1.3 Treatment arms/group

At baseline, all eligible subjects will be randomized to one of the two treatment arms in a 1:1 ratio via Interactive Response Technology (IRT):

- Group 1: 200 AS subjects and 50 nr-axSpA subjects ; These subjects will receive secukinumab 6 mg/kg i.v. at randomization (i.e. BSL), followed by the administration of secukinumab 3 mg/kg i.v. every four weeks starting at Week 4 through Week 48 (exposure through Week 52).
- Group 2: 200 AS subjects and 50 nr-axSpA subjects ; These subjects will receive i.v. placebo at randomization (i.e. BSL) and at Weeks 4, 8, and 12, followed by the administration of secukinumab 3 mg/kg i.v. at Week 16 and every four weeks through Week 48 (exposure through Week 52).

All subjects will receive blinded treatment every four weeks starting at baseline and until Week 16. At Week 16, subjects from Group 1 will continue using secukinumab 3 mg/kg i.v. and subjects from Group 2 will start receiving secukinumab 3 mg/kg i.v. every four weeks (see [Figure 3-1](#)).

Treatment will be provided open-label from Week 16 onwards, as all subjects will be receiving 3 mg/kg i.v. every 4 weeks; however, the investigators, site personnel, subjects and monitors will remain blinded to initial randomized group assignment.

6.1.4 Treatment duration

The planned duration of treatment is 52 weeks. Subjects may be discontinued from treatment earlier (see [Section 9.1.1](#)) due to unacceptable toxicity, disease progression and/or at the discretion of the investigator or the subject.

6.2 Other treatment(s)

No additional treatment beyond investigational drug is provided in this trial.

6.2.1 Concomitant therapy

The investigator should instruct the subject to notify the study site about any new medications (including over-the-counter drugs, calcium and vitamins) administered after the subject was enrolled into the study. All medications (other than study treatment), procedures and significant non-drug therapies (including physical therapy and blood transfusions) must be recorded on the Prior and Concomitant medications or Procedures and Significant Non Drug Therapy eCRF. The reason, name of the drug, procedure or non-drug therapy should be listed.

Guidelines for the use of specific medications are provided below:

Methotrexate (MTX)

Subjects taking MTX (up to 25 mg/week) must be on a stable dose for at least 4 weeks before randomization and maintained stable until Week 16.

Folic acid

Subjects on MTX must be taking folic acid supplementation before randomization and during the trial to minimize the likelihood of MTX associated toxicity.

Systemic corticosteroids

Treatment with systemic corticosteroids is permitted up to a maximum daily dosage of 10 mg prednisone equivalent and if the dose was stable within the 2 weeks preceding randomization. The subject should remain on a stable dose until Week 16.

Corticosteroid dose reductions below 10 mg prednisone equivalent are permitted after Week 16, although the corticosteroid dose should not be reduced more than 1 mg prednisone equivalent every 4 weeks.

Any change in the dose of systemic corticosteroids during the trial must be recorded on the corresponding eCRF page.

Intra-articular corticosteroids are not permitted within the 4 weeks preceding randomization and up to Week 16. After Week 16, no more than 1 joint per 24-week period may be injected. No single injection should exceed 40 mg of triamcinolone (or equivalent) and the total dose of intra-articular corticosteroid may not exceed 80 mg of triamcinolone (or equivalent) during any 52-week period. Injection of intra-articular steroids is not permitted within 8 weeks prior to Week 52.

Non-steroidal anti-inflammatory drugs (NSAIDs) (including COX-1 or COX-2 inhibitors), low strength opioids and acetaminophen/paracetamol

Subjects on regular use of NSAIDs or paracetamol/acetaminophen should be on stable dose for at least 2 weeks before randomization to allow inclusion in the study.

Subjects taking NSAIDs, low strength opioids or paracetamol/acetaminophen PRN within the 2 weeks before randomization can continue to do so in the study; however, they have to refrain from any intake during at least the 24 hours before a visit with disease activity assessment. Regular dosing with low strength opioids is not permitted.

After the Week 16 assessments are completed, a change in the NSAID intake regimen is permitted.

Any change of the NSAID/paracetamol/acetaminophen treatment during the trial should be recorded on the corresponding eCRF page.

6.2.2 Prohibited medication

Use of the treatments displayed in [Table 6-1](#) is NOT allowed after the start of the washout period unless specified otherwise below. Live vaccines should not be given until 12 weeks after last study treatment administration.

Table 6-1 Prohibited medication

Medication	Washout period (before randomization)	Action (after randomization)
Any biologic drugs, including but not limited to TNF α inhibitors, secukinumab, or other biologic drugs targeting IL-17 or IL-17 receptor Etanercept Infliximab Adalimumab, golimumab, certolizumab	Biological immunomodulating agents > 3 different TNF α Inhibitors: never 4 weeks 8 weeks 10 weeks	Discontinue investigational treatment
Any cell-depleting therapies including but not limited to anti-CD20 or investigational agents [e.g., alemtuzumab (Campath), anti-CD4, anti-CD5, anti-CD3, and anti-CD19]	Never	Discontinue investigational treatment
Conventional synthetic DMARDs (with the exception of MTX and sulfasalazine) and ts-DMARDs including apremilast, tofacitinib, etc.	4 weeks	Discontinue investigational treatment
Leflunomide	8 weeks	Discontinue investigational treatment
Leflunomide with cholestyramine washout [#]	4 weeks	Discontinue investigational treatment
Any investigational treatment or participation in any interventional trial	4 weeks or 5 half-lives (whichever is longer)	Discontinue investigational treatment
Unstable dose of NSAIDs (including selective COX-1 and COX-2 inhibitors)	2 weeks	Dose adjustments allowed after Week 16 Discontinuation of investigational treatment may be required on a case by case basis.
Analgesics other than NSAIDs, paracetamol/acetaminophen, and low strength opioids PRN ⁺	2 weeks	Discontinue investigational treatment

Medication	Washout period (before randomization)	Action (after randomization)
Systemic corticosteroids > 10 mg prednisone equivalent (until Week 16)*	2 weeks	If administered due to a medical urgency unrelated to the patient's arthritis, study treatment should be interrupted until the steroid is discontinued. If not administered for a medical urgency or for use related to the patient's arthritis, then discontinuation of investigational treatment may be required on a case by case basis
Unstable dose of systemic corticosteroids ≤ 10 mg prednisone equivalent (until Week 16)*	2 weeks	Discontinue investigational treatment (Dose adjustments allowed after Week 16) Discontinuation of investigational treatment may be required on a case by case basis.
Intra-articular corticosteroids injections (until Week 16)*	4 weeks	Discontinue investigational treatment
Intramuscular or intravenous corticosteroid treatment	4 weeks	Discontinuation of investigational treatment may be required on a case by case basis
Live vaccinations	6 weeks	If administered due to a medical urgency, study treatment should be interrupted for 4 months. If administered not for a medical urgency then discontinue investigational treatment

* See details about corticosteroid management in [Section 6.2.1](#).

† Regular dosing with low strength opioids is not permitted.

#In case of leflunomide treatment, a drug wash-out of 8 weeks must be performed. Another wash-out procedure might also be considered. Cholestyramine could be given orally to wash-out the drug at a dose of 8 g t.i.d. Cholestyramine reduced plasma levels of the active leflunomide metabolite by approximately 40 % in 24 hours and by 49 % to 65 % in 48 hours in three healthy volunteers. The administration of cholestyramine is recommended in subjects who require a drug elimination procedure. If a subject receives 8 g t.i.d. for 11 days he/she can be safely randomized 4 weeks after the beginning of the 11-day treatment period.

6.2.3 Rescue medication

Rescue medication is defined as any new therapeutic intervention or a significant change to ongoing therapy made because a subject is experiencing either no benefit from participation in the trial or worsening / exacerbation of his/her disease.

Rescue medication should not be used before completion of Week 16 assessments (see [Table 8-1](#)). Although no subject will be restricted from receiving necessary rescue medications for

lack of benefit or worsening of disease, if rescue with prohibited biologics (as described in [Section 6.2.2](#)) occurs prior to completion of Week 16 assessments, subjects will be discontinued from study treatment and enter into the follow-up period after an end of treatment visit. Efficacy will be assessed in detail at every study visit, and subjects who are deemed not to be benefiting from the study treatment based upon safety and efficacy assessments by the investigator or for any reason on their own accord will be free to discontinue participation in the study at any time.

Changes in concomitant therapy with NSAIDs are permitted after Week 16 assessments as per investigator's clinical judgment. After Week 16, the dose and regimen of other concomitant medications may be adjusted slowly at the investigator's discretion and recorded appropriately on the CRF page.

Any use of rescue medication must be recorded in the Prior/Concomitant medications eCRF.

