9.1 Discontinuation

9.1.1 Discontinuation of study treatment

Discontinuation of study treatment for a subject occurs when study treatment is stopped earlier than the protocol planned duration and can be initiated by either the subject or the investigator.

The investigator must discontinue study treatment for a given subject if, he/she believes that continuation would negatively impact the subject's well-being.

The following circumstances **require** study treatment discontinuation:

- Withdrawal of informed consent (WoC)
- Emergence of the following adverse events:
 - a. Any severe or serious adverse event that is not compatible with administration of study medication, including adverse events that require treatment with an unacceptable co-medication
 - b. Onset of lymphoproliferative disease or any malignancy except for treated basal cell carcinoma, treated actinic keratoses, treated in situ carcinoma of the cervix or non-invasive malignant colon polyps which are being or have been removed
 - c. Life-threatening infection
 - d. Severe hypersensitivity reaction or anaphylactic reaction
- Any laboratory abnormalities that in the judgment of the investigator are clinically significant and are deemed to place the subject at a safety risk for continuation in the study (A general guidance on clinically notable laboratory values is provided in [Section 16.1](#).)
- Pregnancy
- Use of any biologic immunomodulating agent except secukinumab
- Any protocol deviation that results in a significant risk to the subject's safety

In addition to these requirements for study treatment discontinuation, the investigator should discontinue study treatment for a given subject if there is a lack of improvement or worsening of their symptoms, or if on balance, he/she thinks that continuation would be detrimental to the subject's well-being.

If discontinuation of study treatment occurs, the investigator should make a reasonable effort to understand the primary reason for the subject's premature discontinuation of study treatment and record this information.

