12.4.2 Statistical model, hypothesis, and method of analysis

The estimand for primary endpoint is defined as follows:

- A. Population: defined through appropriate inclusion/exclusion criteria to reflect the targeted axSpA population (AS and nr-axSpA)
- B. Variable: composite of remaining on the study and on randomized treatment through 16 weeks and achieving ASAS40 response at 16 weeks
- C. Intercurrent event: the intercurrent event is captured through the variable definition
- D. Population-level summary: difference in proportions of responders between the secukinumab and placebo arms

The statistical hypothesis for ASAS40 being tested is that there is no difference in the proportion of subjects fulfilling the ASAS40 criteria at Week 16 in the secukinumab i.v. regimen versus placebo regimen.

Let p_0 denote the proportion of ASAS40 responders at Week 16 for placebo regimen and p_1 denote the proportion of ASAS40 responders at Week 16 for secukinumab i.v. regimen.

In statistical terms, $H_1: p_1 = p_0$, $H_{A1}: p_1 \neq p_0$, i.e.,

H_1 : secukinumab i.v. regimen is not different to placebo regimen with respect to ASAS40 response at Week 16

The primary analysis will be conducted via logistic regression with treatment and stratification factor (disease condition) as factors and weight as a covariate. Difference in marginal response proportions with p-value and 95% confidence interval (CI) will be presented comparing secukinumab i.v. regimen to placebo.

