12.4.3 Handling of missing values/censoring/discontinuations

Missing data for ASAS40 response and other binary efficacy variables (e.g., ASAS 5/6, etc.) for data up to Week 16 will be handled as follows:

1. Patients who drop out of the trial for any reason will be considered as non-responders from the time they drop out through Week 16
2. Patients who do not have the required data to compute responses (e.g., ASAS components) at baseline and at the specific timepoint will be classified as non-responders at the specific timepoint.

Patients who are unblinded prior to the scheduled time point will be considered non-responders from the time of unblinding up to Week 16. The primary analysis will use the non-responder imputation.

Continuous variables (e.g., ASAS components) will be analyzed using a mixed-effects model repeated measures (MMRM) which is valid under the missing at random (MAR) assumption. As such, single-point imputation of missing data will not be performed (e.g., LOCF). For analyses of these parameters, if all post-baseline values are missing then these missing values will not be imputed and this patient will be removed from the analysis of the corresponding variable, i.e., it might be that the number of patients providing data to an analysis is smaller than the number of patients in the FAS.

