12.4.4 Sensitivity and Supportive analyses

Sensitivity analyses and supportive analyses will be conducted in order to provide evidence that the results seen from the primary analysis are robust. These analyses will center on the deviations in model assumptions and the treatment of missing data.

In order to determine the robustness of the logistic regression model used for the primary analysis, ASAS40 response at Week 16 will also be evaluated using a non-parametric ANCOVA model (Koch et al 1998) with the same independent variables as the logistic regression model. In addition, further logistic regression models may be conducted which explore the impact of other baseline or disease characteristics (and respective interactions with treatment group) on response.

The impact of missing data on the analysis results of ASAS40 will be assessed as well by repeating the logistic regression model using different ways to handle missing data.

These may include, but are not limited to:

- Multiple imputation
- Observed data analysis
- Tipping point analysis

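### A subject rescued before Week 16 and kept on study treatment counts as an ASAS40 responder if the criteria are met, because neither the primary estimand nor the non-responder rules mention rescue

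*Protocol*

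**What the plan says.** Protocol section 3 (repeated in SAP 1.1) does not allow rescue until Week 16. Section 6.2.3 is softer: "Rescue medication should not be used before completion of Week 16 assessments". It then recognises that rescue may be needed, in a sentence that opens "Although no subject will be restricted from receiving necessary rescue medications for" lack of benefit or worsening. That sentence requires study treatment to stop if the rescue is a prohibited biologic. The definition is wide: "Rescue medication is defined as any new therapeutic intervention or a significant change to ongoing therapy" made because the subject has no benefit or is getting worse. Section 6.2.3 allows NSAID changes, and slow adjustment of other background drugs, only after Week 16. Use of rescue must be recorded.

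The primary variable in 12.4.2, item B, is a "composite of remaining on the study and on randomized treatment through 16 weeks and achieving ASAS40 response at 16 weeks". Item C adds that "the intercurrent event is captured through the variable definition". Section 12.4.3 starts its non-responder rules with "Patients who drop out of the trial for any reason will be considered as non-responders from the time they drop out through Week 16", then adds subjects without the data needed and subjects unblinded early. Of the sensitivity and supportive analyses, 12.4.4 says: "These analyses will center on the deviations in model assumptions and the treatment of missing data". Its list is open but names nothing on rescue. Item B for the secondary binary variables in 12.5.1 follows the same pattern as the primary one.

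**The concern.** The plan chose a composite estimand in which leaving randomized treatment is failure. Rescue for lack of benefit while staying on treatment is an event that the protocol itself foresees, and the composite says nothing about it. Read literally, a response reached with the help of an added steroid or a raised NSAID dose is credited to the randomized arm.

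Two things are at stake. The first is what the difference in proportions means: item C says intercurrent events are dealt with, and this one is not. The second is consistency. For several rescue drugs, stopping study treatment is a case-by-case decision. Two subjects with the same rescue and the same Week 16 scores can therefore be classified differently, depending on whether treatment was stopped.

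**Working it through.** **Step 1. Which rescue is already non-response?** Table 6-1 requires a stop for biologics, cell-depleting agents, leflunomide, other conventional synthetic and targeted synthetic DMARDs, analgesics outside the permitted ones, and intra-articular steroid before Week 16. Those subjects fail item B, so there is no gap for them.

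**Step 2. Which rescue can leave a subject on treatment?**
- Unstable NSAID dose, arthritis-related systemic steroid above 10 mg, and intramuscular or intravenous steroid. Table 6-1 prohibits these, but a stop is only case by case. For unstable steroid at or below 10 mg it gives both instructions, to stop and to decide case by case.
- Methotrexate and sulfasalazine. Both are exempt from the DMARD row. Section 6.2.1 holds methotrexate stable to Week 16 but states no consequence for a change.
- Regular paracetamol. It is exempt from the analgesic row, and no action is listed.

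**Step 3. How is such a subject classified?** On study: yes. On randomized treatment: yes. ASAS40 met: yes. Dropped out, missing data or unblinded: no. Result under 12.4.2 and 12.4.3: responder.

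**Step 4. How large could the effect be?** Inputs from 12.8.1: 250 per arm, 28.2% on placebo, 44.9% on secukinumab, two-sided 5%, chi-square test, stated power about 96%.

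Power = Φ[(d − 1.96·s0)/s1], with s0 = √(2·p̄(1−p̄)/250) and s1 = √(p0(1−p0)/250 + p1(1−p1)/250).

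The plan's own figure: d = 0.167, p̄ = 0.3655, s0 = 0.0431, s1 = 0.0424, so power = Φ(1.947) = 97.4%. With continuity correction it is 96.8%. The stated figure reproduces.

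Let r0 and r1 be the proportions rescued and kept on treatment, on placebo and secukinumab, and f the proportion of them who meet ASAS40. None of these is in the documents, so all values below are assumptions. If the planned rates treat rescue as non-response, counting these responses gives p0 = 28.2% + r0·f and p1 = 44.9% + r1·f. The difference falls by (r0 − r1)·f.

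| r0 | r1 | f | placebo | secukinumab | difference | power |
|---|---|---|---|---|---|---|
| 5% | 2% | 10% | 28.7% | 45.1% | 16.4 | 96.9% |
| 5% | 5% | 10% | 28.7% | 45.4% | 16.7 | 97.4% |
| 10% | 5% | 20% | 30.2% | 45.9% | 15.7 | 95.3% |
| 15% | 2% | 10% | 29.7% | 45.1% | 15.4 | 94.7% |
| 2% | 5% | 20% | 28.6% | 45.9% | 17.3 | 98.1% |

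In the first row, 250 × 5% × 10% = 1.25 placebo subjects and 250 × 2% × 10% = 0.5 secukinumab subjects change status.

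Section 12.8.1 does not say whether the planned rates already include rescued responders. If they do, planned power stands and a non-responder rule moves the rates down instead. With the first row's assumptions, placebo becomes 28.2 − 0.5 = 27.7% and secukinumab 44.9 − 0.2 = 44.7%, a difference of 17.0 points.

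**The case against.** The best case on the other side is that the plan closes most of this route before the analysis. Rescue is not allowed until Week 16. The case-by-case drugs are prohibited, and only the consequence is left open. The wording in 6.2.3 on changes after Week 16 implies that other background doses are held until then, and 6.7.1.2 monitors stable methotrexate, sulfasalazine, NSAID and paracetamol doses. Section 9.1.1 adds that "the investigator should discontinue study treatment for a given subject if there is a lack of improvement or worsening of their symptoms", which would make the subject a non-responder.

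Rescue may also achieve little. Section 1.1 describes conventional DMARDs as largely ineffective in NSAID-refractory AS. Inclusion criterion 9 asks for inadequate response to at least two NSAIDs, or withdrawal for intolerance, toxicity or contraindication. As-needed NSAID and paracetamol are barred for 24 hours before assessments. Steroid is the main plausible exception.

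All of this stands as a reason to expect few cases. It does not say how a case is analysed. The instruction in 9.1.1 is a 'should' and lies outside that section's list of required stops.

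Counting responses regardless of rescue would be a legitimate strategy, but the plan does not state it. It would also sit oddly beside a composite that treats stopping as failure. A separate Week 16 analysis plan might hold a rule. The SAP supplied does not restate the primary analysis (2.5) and declares no change from the protocol (section 4).

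A reader might infer that early rescue is freely open. Section 3 and Table 6-1 contradict that.

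**Conclusion.** The gap is real but narrow. It concerns subjects rescued although rescue is not allowed, kept on treatment despite 9.1.1, and meeting ASAS40 at Week 16. The stated rules make them responders. Their number is unknown and probably small. With 5% against 2% rescued and 10% of them responding, the effect is 0.3 points and half a point of power.

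A reader might infer a serious loss of power. With 15% against 2% rescued, a 28.2% response among them would give 13.0 points and 85.0% power, and a 44.9% response would give 10.9 points and 69.8%. The documents support neither. That rescue rate exceeds the whole 10% drop-out anticipated in section 5, and those response rates are the planned ones for whole arms, applied here to subjects selected for lack of benefit.

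Nor does the gap point to a false positive. If placebo subjects are rescued more often, which is the likelier pattern for an effective drug, the difference shrinks. The documents do not fix the direction, though: with more rescue on secukinumab it would grow.

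The reason to act is a clear estimand and a fixed rule, at little cost, rather than a threat to the primary test.

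**What to change.** Add a rule to 12.4.3. Subjects who receive rescue as defined in 6.2.3 before the Week 16 assessment are non-responders from that date. Rescue here means a new or increased NSAID, regular paracetamol, methotrexate, sulfasalazine, or systemic corticosteroid (including intramuscular or intravenous), recorded as given for lack of benefit or worsening. Classify subjects from the recorded medication and reason before unblinding, because whether a change counts as rescue needs some judgement.

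Add matching words, such as 'without rescue', to item B of 12.4.2 and to item B for binary variables in 12.5.1. In 12.4.4, name a repeat of the primary model with ASAS40 as observed regardless of rescue.

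The cost is one rule, one extra model run and short wording edits. Sections 6.2.1 and 6.2.3 already require the medication, its reason and any rescue use to be recorded. The downside is that some rescued subjects who would have responded anyway become non-responders; the as-observed analysis shows how much that matters.
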